6.3 Population / Sample size including power calculation

Sample size:

The sample size will be 20 children, 10 in each group.

Sample size calculation:

Sample size calculator used: https://www.ai-therapy.com/psychology-statistics/sample-size-calculator)

This pilot RCT is the first to use ReST with children with CP in a randomised controlled trial. There are no previous studies of this intervention with this population using the proposed outcome measures from which sample sizes could be calculated, so studies with similar populations, treatments, and measures were considered for sample size calculations. ReST is a motor speech intervention for the treatment of childhood apraxia of speech (CAS). While it has been shown to be effective in improving speech in children with CAS, it has not been researched with children with CP. Our exploratory pilot study on the use of ReST with children with CP indicated improvement in mean length of utterance, with a d2 effect size of 0.56. This effect size gives a sample size of 6. This was derived from calculating the effect sizes from the group means (baseline and maintenance), and standard deviation for four outcome measures. Speech MLU is a secondary outcome in the current study ReST effect sizes have primarily been calculated using d2. Using this metric, Thomas (2017) reported an average ReST intervention effect size of 5.55 (SD 2.41, range 2.48-8.52). (Previously published single-case clinician-delivered ReST treatment studies reporting similar dependent measures; McCabe et al., 2014; Thomas et al., 2014; Thomas et al., 2016). Using this effect size with a power of 0.8 and alpha of 0.05 the online sample size calculation produced a sample size of **3 for each group**. The only other RCT using ReST in children with CAS produced an effect size (Cohen's d) of 1.376 giving a sample size of 10 for each group.

The other motor speech interventions used with children with CP include LSVT LOUD (Boliek & Fox, 2017), Speech Systems Intelligibility Treatment (Pennington et al., 2010; 2013), and PROMPT (Ward, 2012). Sample size calculations were derived for each of these studies.

LSVT LOUD: Boliek & Fox, 2017 reported a Cohen's d effect size of 0.3 for pre and post speech intelligibility measures. The sample size calculation was therefore a sample size of 52.

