Speech Systems Intelligibility Treatment: Effect sizes were not reported in these studies, so they were calculated from the published study data. These were (Pennington et al., 2010) Cohen's d effect size of - 0.5 and (Pennington et al., 2013) 0.6 respectively. The sample size calculation was based on these provided sample sizes of 19 and 23 respectively.

PROMPT: Ward (2012) reported a Cohen's d effect size for the percentage of phonemes correct each of the four children. The mean of these was 1.1. The sample size calculation was therefore 7.

The sample size figures calculated from the non-ReST studies on children with CP were notably larger than those based on the ReST treatment studies. Although studies on children with CP may require a large sample size due to their heterogeneity, a sample size that is too large may be presumptuous at this stage as the effectiveness of ReST with children with Cerebral palsy is not known. Besides, the interventions in these studies differed quite significantly from ReST intervention, which may render the sample sizes improbable. In the absence of previous comparable studies on the effectiveness of ReST in children with CP, studies with other populations using ReST, studies with CP population using different interventions, and an exploratory study on ReST with CP population were considered in sample size calculations. Based on these, and our best estimate, a sample size of six per group was satisfactory. This was increased to ten per group to account for potential attrition and to reflect the calculation from Murray et al. (2015) study on the effectiveness of ReST.

Page 10 of 21 The effectiveness of Rapid Syllable Transition Treatment in improving communication in children with cerebral palsy: A randomized controlled study

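### Section 6.3 enters a single-case effect size (d2 of 5.55) as a two-group Cohen's d, so its 3 per group is not a valid sample size, and the 6 from the pilot value of 0.56 does not reproduce

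*Protocol*

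**What the plan says.** Protocol section 6.3 assembles effect sizes from several sources, converts each to a sample size, and then forms an overall judgement. Three of its lines concern ReST.

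- **Single-case studies.** The protocol notes that "ReST effect sizes have primarily been calculated using d2", and on that metric an earlier source "reported an average ReST intervention effect size of 5.55 (SD 2.41, range 2.48-8.52"). It describes the underlying work as "Previously published single-case clinician-delivered ReST treatment studies reporting similar dependent measures". The calculation is introduced with the words "Using this effect size with a power of 0.8 and alpha of 0.05 the online sample size calculation produced a sample size of", and the result printed there is "3 for each group".
- **Pilot in children with CP.** Mean length of utterance, a secondary outcome here, improved with an effect of 0.56. The value is labelled d2 but is said to come from group means at baseline and maintenance and a standard deviation. It is converted to a sample size of 6.
- **ReST randomised trial in childhood apraxia of speech.** The effect of 1.376 is labelled Cohen's d, "giving a sample size of 10 for each group".

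The section then compares the sources: "The sample size figures calculated from the non-ReST studies on children with CP were notably larger than those based on the ReST treatment studies". It weighs all of them together with the team's best estimate, accepts six per group as enough, and raises this to ten per group to allow for attrition and to match the calculation from the ReST randomised trial.

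**The concern.** A two-group sample-size calculation needs the difference between two group means divided by the standard deviation between children. A single-case study has no comparison group, so whatever its effect size measures, it is not that ratio. The protocol itself uses two labels, d2 for the single-case average and Cohen's d for the randomised trial, yet passes both through the calculator as if they were the same thing.

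The pilot line has a different fault. An effect of 0.56 is smaller than 1.376, yet it is said to need fewer children (6 against 10). With the same power and alpha, a two-group calculation cannot give that ordering.

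The 3 and the 6 are two of the three ReST-based figures and form part of the stated basis for accepting six per group. A reader or ethics committee could conclude from them that three to six children per group would be adequate for a comparison of ReST with usual care, and that ten leaves a comfortable reserve for drop-out. Neither conclusion holds.

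**Working it through.** **Inputs, all from protocol section 6.3.** Power 0.80; alpha 0.05; effect sizes 5.55 (d2, single-case), 0.56 (labelled d2, pilot) and 1.376 (Cohen's d, randomised trial); planned n of 10 per group. Sidedness is not stated, so two-sided is assumed. Power and alpha are stated for the 5.55 line and are assumed to apply to the other two.

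**Formulas.** Two-sample t with n per group: degrees of freedom 2n − 2, noncentrality d × √(n/2). Paired t with n children: degrees of freedom n − 1, noncentrality d × √n. Power is the probability that the noncentral t variable falls outside the two-sided 5% limits.

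**Step 1: reproduce the printed figures (two-sample t).**
- d = 5.55, n = 2: noncentrality 5.55 × √1 = 5.55, power 78.8%.
- d = 5.55, n = 3: noncentrality 5.55 × √1.5 = 6.80, power 99.8%. The smallest adequate n is 3, as printed.
- d = 1.376, n = 9: noncentrality 1.376 × √4.5 = 2.92, power 78.2%.
- d = 1.376, n = 10: noncentrality 1.376 × √5 = 3.08, power 82.9%. The smallest adequate n is 10, as printed.

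The 1.376 line identifies the method: a one-sided two-sample test would give 8, and a paired two-sided test 7. So 5.55 was very probably entered as a two-group Cohen's d.

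**Step 2: the pilot value of 0.56.**
- Two-sample t: 51 per group gives just under 80% (79.97%) and 52 gives 80.7%, so 52 per group.
- Paired t: 27 children give just under 80% (79.98%) and 28 give 81.5%, so 28 children.
- One-sided versions: 41 per group (two-sample) and 22 children (paired).
- At the printed 6, power is 14% (two-sample, 6 per group) or 20% (paired, 6 children), both two-sided.

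None of these variants gives 6.

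**Step 3: what each group size delivers (two-sample t, two-sided).**

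| n per group | Power at d = 1.376 | d detectable at 80% power |
|---|---|---|
| 3 | 26% | 3.07 |
| 6 | 58% | 1.80 |
| 9 | 78% | 1.41 |
| 10 | 83% | 1.32 |

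The value 1.376 needs all ten children per group. With one loss per group, power falls below 80%.

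**The case against.** The strongest reply is that nothing in the trial depends on the 3. The final ten per group is tied to the randomised-trial value, 1.376 alone yields 10, and nobody proposes to run three per group. That stands, and it limits the point to correcting the stated justification.

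Four stronger readings are tempting, and the documents do not support them.

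- **That d2 is a fixed multiple of Cohen's d.** A reader might set 5.55 against 1.376 and infer a scale about four times too large (5.55 / 1.376 = 4.03). The two values come from different studies and designs, and by its title in the reference list the randomised trial compared ReST with another active programme. The ratio mixes metric, design and comparator. The documents also give no formula for d2, so the argument rests only on the separate labels and the single-case design of the sources.
- **That the pilot 0.56 has the same metric fault.** It carries the d2 label, but the protocol says that it was derived from group means and a standard deviation, which describes a group-level before-after effect. What is demonstrably wrong there is the conversion to 6.
- **That the printed PROMPT figure of 7, being below 10, undoes the contrast between CP-study and ReST sizes.** The PROMPT value of 1.1 is itself a mean of per-child values, and the two-group method that turns 1.376 into 10 gives 15 for it. The other printed CP-study figures (52, 19 and 23) all exceed 10. The comparison quoted above is therefore not overturned, and there is no case here for removing it.
- **That the 3 is the stated reason for setting the CP-study figures aside.** The protocol's reasons are that the effectiveness of ReST in CP is unknown and that the other interventions differ from ReST.

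**Conclusion.** The point holds in a limited form. The 3 per group is not a valid sample size, because an effect from studies without a between-group contrast was used as a between-group Cohen's d. The 6 from 0.56 is a separate error of calculation: the figure should be 52 per group (two-sample) or 28 children (paired). The acceptance of six per group therefore lacks support; six gives 58% power even at 1.376.

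The planned size does not change. Ten per group follows from 1.376 with 83% power, provided that all ten children per group contribute data. The protocol also asks the same ten to absorb attrition, without giving a rate, and the calculation leaves almost no room for that: nine per group gives 78%.

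These results assume a two-sided 5% test, equal groups, a plain comparison of two means, and 1.376 taken as a between-group standardised difference, as its label and its source in a randomised trial suggest. They do not show that 1.376 is a realistic effect for intelligibility in children with CP.

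**What to change.** In section 6.3:

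1. Delete the calculation that leads from 5.55 to 3 per group. The single-case results can stay as background, without a sample size attached.
2. Delete the 6 attributed to 0.56, or replace it with the recalculated figure (52 per group two-sample, or 28 children paired) and name the test used.
3. Drop the statement that accepts six per group.
4. State that ten per group rests on the ReST randomised-trial value (Cohen's d 1.376, 83% power, two-sided alpha 0.05), and that it detects a between-group d of about 1.32 at 80% power only with no attrition. With nine per group the detectable d is about 1.41, and power at 1.376 is 78%.

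The cost is a few sentences and no additional children; the sample size stays at 20. The justification will look less generous, because its two smallest figures go and the lack of reserve for attrition becomes visible.

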6.4 Participant Enrolment and Randomisation 6.4.1 Recruitment

Participants will be recruited by CP Alliance therapy sites in Sydney, Central Coast, and Central West. Recruitment will also be from the NSW CP register. The study will be advertised at Cerebral Palsy Alliance centres on notice boards, social media (Facebook and Twitter), and through contact with treating therapists. The study flyer will direct interested potential participants to contact the study coordinator, [name]. When families contact the study coordinator, they will be informed about the purpose of the study and provided with the Participant Information Sheet. An opportunity to ask questions will be provided, and unless eligibility can be determined from reports, arrangements will be made to meet with the child (teleconferencing or in person) to determine eligibility. The study coordinator will then advise the family if their child satisfies the inclusion criteria.

6.4.2 Inclusion and Exclusion Criteria

Inclusion criteria

- 1) Aged between 8-14 years
- 2) Diagnosis of CP
- 3) Viking Speech Scale classification II-III
- 4) No diagnosed intellectual disability
- 5) normal or adjusted-to-normal hearing and vision

Exclusion criteria

- 1) non-CP diagnoses or multiple diagnoses
- 2) intellectual disability
- 3) Viking Speech Scale classification I or IV

6.4.3 Informed consent process

The informed consent process involves the following:

Interested parents will contact the study coordinator or one of the other researchers. They will be provided with the Participant Information Sheet and the Participant Consent Form. Parents will be encouraged to ask questions about the research and the risks and benefits of participation.

The families are informed that their participation is completely voluntary. They are free to decline to attend the study, and also free to withdraw from the study at any time. This will have no implications on their relationship with the research team, the University of Sydney, or Cerebral Palsy Alliance.

The families will be provided the name and contact details of the Principal Investigator and the University of Sydney ethics committee if they have any questions, concerns or complaints about the study. The families will also be provided with the study coordinator's details unless they already have them.

6.4.4. Screening and eligibility

Eligibility on the diagnosis of CP, cognition, and hearing and vision will be determined based on medical reports. The Viking Speech Scale (VSS) level will be determined from reports created within the last 18 months or a screening assessment.

The study coordinator will meet with the child (teleconferencing or in person) to determine the VSS level. Where the VSS level is not clear, a second person from the research team will meet with the child via teleconference. The decision on eligibility will be based on a consensus between the two research team members.

Information on the children's diagnosis, cognitive level, hearing, and vision will be sought from reports at school entry. If the family does not have these reports, information will be searched from Cerebral Palsy Alliance medical records and the Cerebral Palsy CP Register with the family's consent.

6.4.5 Randomisation and Blinding Processes

Randomization

Participant randomization flowchart

After the Informed Consent Form is signed and the baseline assessment has been completed, an officer not connected with the study and at a separate location draws a concealed opaque envelope from a group of 20 identical envelopes. Each envelope contains the group allocation. The officer will inform the study coordinator who informs that family.

Children will be randomly allocated to one of;

1. A ReST first group who will receive ReST 3 days per week for 6 weeks, for a total of 18 sessions.

2. A usual care group who will receive usual care first and ReST after Treatment phase 1 Follow up assessment, T3 assessment.

Blinding

Blinding of the treating clinicians or the participants is not possible as this is a behavioural RCT. The treating clinicians are not able to deliver the intervention without knowing about it. The participants will not be blinded to the study treatment as they will know from recruitment that the treatment aims to improve speech. The clinicians scoring the assessments will be blinded to group allocation.

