6.2 Schedule of Events/ Treatment Phases

Table 1: Flowchart of the schedule of events

- 1. Rolling Recruitment: Please see section 6.4.1
- 2. Eligibility Screening: Participants will participate a screening assessment via teleconferencing. This will take 10 15 minutes.
- 3. **Baseline Assessment, T1**: All eligible participants will attend an initial assessment in person at the University speech pathology clinic or at the family's home. If this is not possible, the assessment will be conducted on teleconference.
- 4. The Consent form will be signed.
- 5. **Randomisation**: The children who are eligible to participate will be randomised to ReST first- group or usual care- group.
- 6. Treatment phase 1:
 - a. **ReST first- group:** Children in the treatment group will receive ReST therapy three times a week for six weeks, totalling 18 sessions.
 - b. Usual care- group: Children in the usual care group will continue their usual care therapy and complete T2 and T3 assessments. See Table 1, The Flowchart of the schedule of events. The content and dosage of usual care will be recorded. If the participant has a speech generating device, the frequency of use and device satisfaction will also be recorded.
- 7. **Treatment phase 1 Post intervention assessment, T2**: Within one week after the final ReST session.
- 8. **Treatment phase 1 Follow up assessment, T3:** Three weeks after the final ReST session.
- 9. Treatment phase 2:
 - a. **ReST first- group:** The children will complete T4 and T5 assessments.
 - b. **Usual care- group:** Children in the usual care group will commence ReST after T3 assessments are completed. See Table 1, The Flowchart of the schedule of events.
- 10. **Treatment phase 2 Post intervention assessment, T4**: Within one week after the final ReST session.
- 11. **Treatment phase 2 Follow up assessment, T5**: Three weeks after the final ReST session.

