7.1.2. Participant Benefits

The participants will not be disadvantaged by randomisation as both groups will receive the ReST intervention and all the assessments.

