9. DATA MANAGEMENT

9.1 Data collection and storage

Research data, including video recordings and assessment results are collected in electronic form. Identification codes replace names in all files.

All assessment and treatment sessions are videoed, which will then be uploaded by the treating student therapist to The University of Sydney approved Dropbox immediately after the session.

Paper copies of assessment forms are scanned and collected in electronic form.

Paper copies of intelligibility ratings are scanned and collected in electronic form.

The paper forms are shredded immediately after scanning.

The weekly online questions for the usual care group are collected weekly through REDCap survey and saved electronically.

Consent forms, contact details, and identifying codes will be held in a password protected encrypted file in the RDS.

Once the data is no longer being actively used it will be deleted from Dropbox and only retained in the RDS.

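### Scorers are masked to group but not to assessment occasion, so clinician-scored change over time is open to expectation bias, although the randomised between-group comparison stays protected

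*Protocol*

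**What the plan says.** On scorers, section 6.4.5 says: "The clinicians scoring the assessments will be blinded to group allocation". It mentions no masking to visit, date or time point.

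The sequence of exposure comes from these places:

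- Section 6.4.5 puts allocation later than T1: "After the Informed Consent Form is signed and the baseline assessment has been completed".
- Section 6.2, ReST-first group, phase 1: "Children in the treatment group will receive ReST therapy three times a week for six weeks, totalling 18 sessions". In phase 2, "The children will complete T4 and T5 assessments".
- Section 6.2, usual-care-first group: "Children in the usual care group will commence ReST after T3 assessments are completed".
- Section 7.1.2 confirms that "both groups will receive the ReST intervention and all the assessments".

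On files, section 9.1 says "Identification codes replace names in all files" and "All assessment and treatment sessions are videoed, which will then be uploaded by the treating student therapist". It does not say whether visit or date is removed, or in what order recordings are scored.

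Section 6.14 plans a repeated measures ANOVA of group by time, with Cohen's d for significant comparisons, to compare the treatments over time.

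**The concern.** In a parallel-group trial, masking the scorer to group largely masks treatment. Here it does so only while the two groups differ in exposure, at T2 and T3. At T1, T4 and T5 both groups have the same ReST history, so the visit alone reveals it.

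Judging disordered speech from single words, phonemes or utterances leaves room for expectation. A scorer who knows that a recording follows ReST may, without intending to, hear it as better. The trial is described as a single-blind cross-over and its analysis looks at change over time. A reader would naturally take the usual-care-first group's change after ReST, the time effect and the follow-up scores as blinded evidence. The stated rule does not secure that.

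**Working it through.** The protocol gives no figure on this point to reproduce. The check is a tabulation of exposure, followed by tracing a scoring shift through the contrasts.

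**Step 1. ReST received before each visit** (sections 6.2, 6.4.5 and 7.1.2)

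| Visit | ReST first | Usual care first | Does the visit alone fix exposure? |
|---|---|---|---|
| T1 | no | no | yes |
| T2 | yes | no | no |
| T3 | yes | no | no |
| T4 | yes | yes | yes |
| T5 | yes | yes | yes |

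**Step 2. Count.** With 20 children and five visits there are 20 × 5 = 100 assessments if nobody withdraws. Exposure is fixed by the visit at 20 × 3 = 60 of them. T1 precedes randomisation, as in any trial with such a baseline, so the part specific to this design is T4 and T5: 20 × 2 = 40. Section 6.14 speaks of six time points where section 6.2 schedules five. The count follows the schedule, and the two sections need reconciling.

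**Step 3. Which contrasts does a shift reach?** Set the true effect to zero. Let s1 to s5 be the scoring shift at T1 to T5, the same in both groups because group is masked. Take two patterns:

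- A: the shift occurs only where exposure is certain, s = (0, 0, 0, b, b).
- B: the scorer also applies half the shift when unsure at T2 and T3, s = (0, b/2, b/2, b, b).

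| Contrast | Formula | A | B |
|---|---|---|---|
| Between groups, change from T1 to any visit t | (st − s1) − (st − s1) | 0 | 0 |
| Usual care first, T3 to T4 (before and after ReST) | s4 − s3 | b | b/2 |
| Usual care first, T3 to T5 | s5 − s3 | b | b/2 |
| ReST first, T1 to T2 (before and after ReST) | s2 − s1 | 0 | b/2 |
| Either group, T1 to T4 | s4 − s1 | b | b |
| ReST first, T2 to T5 (maintenance) | s5 − s2 | b | b/2 |
| Either group, T4 to T5 | s5 − s4 | 0 | 0 |
| Within child, ReST minus usual care, usual care first | (s4 − s3) − (s2 − s1) | b | 0 |
| Within child, ReST minus usual care, ReST first | (s2 − s1) − (s4 − s3) | −b | 0 |
| Equal average of the last two rows | | 0 | 0 |

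The between-group contrast is unbiased at every visit, including T4 and T5. So is a cross-over estimate that weights the two sequences equally. Within-group changes that span a change in s are biased.

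**Step 4. Scale, by assumption only.** The documents give no value for b. If it were 0.2 to 0.5 SD, the T3 to T4 change in the usual-care-first group would be inflated by 0.2 to 0.5 SD under A and by 0.1 to 0.25 SD under B. For comparison, section 6.3 cites effects in children with CP of 0.3 for the voice treatment, and of 0.5 (printed with a negative sign) and 0.6 for the speech systems treatment.

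**The case against.** **The hypotheses compare ReST with usual care, and that comparison is intact.** This stands and sets the limit of the point. A reader might infer that the blind protects only the between-group contrast at T2 and T3. It does not stop there: at T4 and T5 a scorer masked to group has no basis for favouring either group, so the shift cancels there too.

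**The visit reveals less than full treatment status.** At T4 it shows that a child has had ReST at some time, but not whether the course has just ended or ended a phase earlier. This stands. The exposure revealed is ReST ever received.

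**The argument is from silence.** The protocol nowhere says that scorers see visit labels, and file handling could be set out in a scoring manual. This stands in part. A reader might conclude that the single-blind description is false. The documents do not support that, since section 6.4.5 explains the blinding as masking to group and nothing contradicts it. But 6.4.5 is where the protocol fixes the masking rule, and the rule it fixes is too narrow for comparisons over time.

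**The shared video storage does not show unblinding.** A reader might infer from section 9.1 that scorers will come across treatment videos and learn the group. The section says nothing about scorers' access or folders, and such access would breach the masking already promised. It supports a precaution only.

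**Many outcomes are not affected by scorer masking.** This also stands. FOCUS is rated by parents, SPAAC is child-directed, and COPM rests on participants' own ratings.

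**Conclusion.** The concern holds in a limited form. Masking to group alone leaves ReST exposure open at T1, T4 and T5 to any scorer who can see the visit or date. On WIPI, percentage of phonemes correct and MLU, this leaves three things unprotected: within-group change (notably T3 to T4 or T5 in the usual-care-first group, and T1 to later visits), the main effect of time, and maintenance to T5 judged against earlier visits. The randomised comparison of ReST with usual care is not threatened.

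The size is b or a fraction of it for the affected contrasts, and b is unknown; the 0.2 to 0.5 SD range is illustrative. The conclusion assumes that scorers can see the visit or date, which the protocol neither states nor rules out. It also assumes that the shift is additive and equal in both groups, that children complete the schedule, and that the three measures named are scored by the masked clinicians. Section 6.5 does not name the scorer of each measure, nor the rater of the ICS, which is therefore left out.

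This is a cheap improvement to the masking rule and does not call the main hypothesis test into question.

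**What to change.** In section 6.4.5, state that outcome scorers are masked both to group and to assessment occasion. To make that work:

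- Score the clinician-scored outcomes from the recordings, which section 9.1 already provides for.
- Give each assessment recording a random code that carries no visit number or date.
- Score the recordings in random order across occasions.
- Keep them in a folder apart from the treatment videos.
- Keep any review of T1 needed to choose ReST targets (section 6.6.1) separate from the blinded outcome scoring, since that review cannot wait until later visits are in.

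The cost is protocol wording, file renaming and a separate folder, with no extra visits. The real drawback is time: scoring in random order across occasions has to wait for later recordings, while section 6.8 has the usual-care-first group finishing by July 2021 and analysis complete by August 2021. A further bar on scorers who have treated or supervised the same child could need extra staff in a study without external funding, so it is not part of this proposal.
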